4.5.2 Immunogenicity Variables

Whole blood will be collected at Day 1, Day 7 and Day 19 to assess vaccine induced IgA antibody responses in lymphocyte secretions by the ALS assay against LTB, CFA/I, CS3, CS5, CS6, and 078 LPS (if sample volume allows). Plasma samples will be collected at Screening, Day 7 and Day 19 to assess vaccine induced IgA antibodies by Enzyme linked immunosorbent assay (ELISA) assay against LTB, CFA/I, CS3, CS5, CS6 and 078 LBS and IgG antibodies by ELISA against LTB and 078 LPS. Fecal samples will be collected at Screening, Day 1, Day 7, Day 19 and Day 29 to evaluate vaccine induced fecal SIgA antibody responses against LTB, CFA/I, CS3, CS5, CS6 and 078 LPS. If insufficient specimen volume is obtained in toddlers, younger children and infants, to measure all antigens, then the five primary antigens (LTB, CFA/I, CS3, CS5, and CS6) will be prioritized.

The immunogenicity variables will be analyzed using the following:

- antibody response defined as ≥ 2-fold increase in antibody titers between baseline and post-immunization.
- antibody response defined as ≥ 4-fold increase in antibody titers between baseline and post-immunization.
- geometric mean titer (GMT)
- geometric mean fold rise (GMFR)

For immunogenicity variables, data inferior to the Lower Limit of Quantification (LLOQ) will be replaced by half the detection limit; data superior to the Upper Limit of Quantification (ULOQ) will be replaced by this limit (truncated data). No search for outliers will be performed. However, the logarithmic transformation will be used as appropriate to improve the distributional properties of the data and reduce the impact of potential outliers.

Flow cytometry will be used to induce T cells responses to vaccine antigens. The percentage of T cells responding to vaccine antigens will be defined for each participant by subtracting the proportion of cells responding to uninfected control cells from the percentage responding to vaccine antigens. In addition, neutralizing antibodies to LTB will be measured and analyzed.

Adequate sampling volume may not be obtained, so the following prioritization scheme will be applied to the vaccine antigens according to analysis as specimen volumes allow:

- ALS IgA: LTB > CFA/I> CS3> CS6 > CS5> 078 LPS;
- Fecal SIgA: LTB > CFA/I> CS3> CS6 > CS5> 078 LPS;
- Plasma IgA: LTB > 078 LPS > CFA/I > CS3 > CS6 > CS5;
- Plasma IgG: LTB > 078 LPS;
- T cell and other immune responses: LTB > CFA/I > CS3 > CS6 > CS5.

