3.3 Study Definitions and Derived Variables

The following definitions and derivations will be used in this study:

 Diarrhea is defined as ≥ 3 unformed or loose stools (mixed liquid and solid components) in a 24 hour period or at least 1 bloody loose or liquid stool or 1-2 liquid stools with at least some dehydration.

- 2. If a participant meets the definition of diarrhea, the start of the diarrhea episode will be the time of the first unformed stool which contributes to meeting the definition and the end of the diarrhea episode will be the time of the last unformed stool. If there is greater than 24 hours between loose or unformed stools then the illness will stop and a new AE will begin.
- 3. Mild diarrhea is defined as at least 3 looser than normal stools without dehydration in a 24 hour period.
- 4. Moderate diarrhea is defined as at least 3 looser than normal stools with dehydration in a 24 hour period.
- 5. Severe diarrhea is defined as at least 3 looser than normal stools with severe dehydration.
- 6. The baseline value will be defined as the last value obtained prior to the first vaccination of study product.
- 7. The reference day will be the day of the first vaccination and will be referred to as Day 1.
- 8. Study days prior to vaccination will be dependent upon the first dose of the vaccine. If the assessment occurred prior to the first dose, study days will be calculated by taking the date minus the first vaccination date (reference day).
- 9. Study days occurring on or after the date of vaccination will be dependent upon when the assessment occurred. If the assessment occurred on or after the first vaccination but prior to the second vaccination, study days will be calculated by taking the date minus the first vaccination date (reference day) and adding 1. If the assessment occurred on or after the second vaccination, then study days will be calculated by taking the date minus the second vaccination date and adding 1.
- 10. Age will be calculated from the date of enrollment and will be presented in whole years for adults and in months for children under 5 years of age (truncated integer).
- 11. The calculations for GMTs will be performed by taking the anti-log of the arithmetic mean of the log₁₀-transformed titers.
- 12. Fold increase/rise will be calculated as the following:
 - a. For fold rise compared to baseline: ratio of: $\frac{post-immunization\ titer}{pre-immunization\ titer}$

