8.1.1 Antibody Response

Percentages of participants with an antibody response at Day 7, Day 19 or at any time point will be calculated along with the corresponding two-sided exact (Clopper-Pearson) binomial 95% CIs. For each antigen, the proportion of participants with an antibody response at Day 7, Day 19 or at any time point will be compared between each pairwise comparison of ETVAX dose level, ETVAX + dmLT dose level, and placebo using Fisher's exact test.

Tables 14.2.1.1 (a)(b)(c)(d) - 14.2.1.2 (a)(b)(c)(d) will summarize the antibody response and 95% CIs for each time period and treatment group by antigen for the FA population and the PP population, respectively. In addition, a Fisher's exact test for each treatment group comparison will be presented for each time period and antigen as shown in Tables 14.2.2.1 (a)(b)(c)(d) - 14.2.2.2(a)(b)(c)(d) for the FA population and the PP population, respectively.

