8.1.2 Geometric Mean Titer

For the ALS titer, antibody levels will be summarized on the original scale by treatment group at Screening, Day 7 and Day 19. The number of observations, geometric mean titer (GMT) and geometric 95% CI of the GMT will be reported. For ALS titers reported as below the assay Lower Level of Quantification (LLoQ), a value of half of the LLoQ will be used. The GMT will be calculated as the antilog of the mean of the logarithms of the ALS titer. The 95% CIs of the GMT will be based on the t-distribution to provide population estimates and will be presented as the antilog. Two-sided 95% CIs for the ratios of post dose 1 and post dose 2 GMTs between two treatment groups will be constructed using the log normal distribution. The log values will be used to construct a CI using the t-distribution for the mean difference between all

pair-wise comparisons. The mean difference and the corresponding CI limits will then be exponentiated to obtain the GMT ratio and the corresponding CI. Each pairwise comparison will be performed on the lognormal assay responses using a t-test. If the values deviate from the log normal distribution, a non-parametric method (i.e., Wilcoxon) may be used for the analysis of the ratio of GMT.

Tables 14.2.3.1 (a)(b)(c)(d) - 14.2.3.2 (a)(b)(c)(d) will summarize the GMTs and 95% CIs for each antigen and treatment group for the FA population and the PP population, respectively. The ratio of GMTs, 95% CI of ratio of GMTs and t-test will be summarized in Tables 14.2.4.1 (a)(b)(c)(d) - 14.2.4.2 (a)(b)(c)(d). Reverse cumulative distribution curves for the ALS titer after the first vaccination (Day 7) and the second vaccination (Day 19) will be presented by treatment group for each antigen analyzed as depicted in Figures 14.2.5.1 (a)(b)(c)(d) - 14.2.5.2 (a)(b)(c)(d).

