8.1.3 Geometric Mean Fold Rise

For the ALS titer, the fold rise will be calculated after the first vaccination (post vaccination 1 antibody titer/baseline antibody titer), after the second vaccination (post vaccination 2 antibody titer/baseline antibody titer), and after the second vaccination compared to first vaccination (post vaccination 2 antibody titer/post vaccination 1 antibody titer). The number of observations, GMFR and 95% confidence intervals for the GMFR will be reported. The GMFR will be calculated as the antilog of the mean of the logarithms of the calculated fold rise. The 95% CIs for the GMFR will be based on the t-distribution to provide population estimates and will be presented as the antilog. Pairwise comparisons of the logs of the fold-rise will be performed using a t-test. If the values deviate from the log normal distribution, a non-parametric method (i.e., Wilcoxon) may be used for the analysis of the fold rise.

Tables 14.2.6.1 (a)(b)(c)(d) - 14.2.6.2 (a)(b)(c)(d) will summarize the GMFRs and 95% CIs for the GMFRs for each antigen and treatment group for the FA population and the PP population, respectively. In addition, the p-value from a t-test for each treatment group comparison will be presented for each time period and antigen as shown in Tables 14.2.7.1 (a)(b)(c)(d) - 14.2.7.2(a)(b)(c)(d) for the FA population and the PP population, respectively.

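### Titres above the ULOQ are set to the ULOQ and then analysed as measured values; where any exceed it, fold rises are capped and ratios between arms are pulled toward 1.

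*SAP*

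**What the plan says.** Section 4.5.2 sets one rule for all immunogenicity variables at the upper end of the assay: "data superior to the Upper Limit of Quantification (ULOQ) will be replaced by this limit (truncated data". It applies to baseline and post-dose titres alike.

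The capped titres feed every immunogenicity summary:

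- **Responders.** Section 4.5.2 has "antibody response defined as ≥ 2-fold increase in antibody titers between baseline and post-immunization" and "antibody response defined as ≥ 4-fold increase in antibody titers between baseline and post-immunization". Section 8.1.1 adds "Percentages of participants with an antibody response at Day 7, Day 19 or at any time point will be calculated"; sections 8.2.1 and 8.3.1 do the same for fecal and plasma antibody.
- **Fold rise.** Section 8.1.3 uses "post vaccination 2 antibody titer/baseline antibody titer", with the baseline fixed in section 3.3: "The baseline value will be defined as the last value obtained prior to the first vaccination of study product". It also takes the ratio of the post-dose 2 to the post-dose 1 titre.
- **GMT ratios.** Section 8.1.2 builds t-based intervals on log titres: "The mean difference and the corresponding CI limits will then be exponentiated to obtain the GMT ratio and the corresponding CI". Sections 8.2.2 and 8.3.2 repeat this.

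Sections 8.1.2, 8.2.2 and 8.3.2 restate the rule for values below the LLOQ but add nothing for values above the ULOQ. The SAP states no ULOQ, no count of truncated values by arm, no censored-data model and no sensitivity analysis for the ceiling.

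**The concern.** A titre above the ULOQ is known only to exceed that limit. Substituting the limit turns a lower bound into an exact observation, with two consequences wherever such titres occur.

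First, a participant with a high enough baseline is a non-responder by construction, whatever the vaccine does, and stays in the denominator. Second, of two arms the one with higher titres loses more to the cap, so the estimated ratio between them moves toward 1.

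The contrasts exposed are those between active arms. Section 3.1.2 makes the dmLT adjuvant effect a secondary objective, and section 2.1 names a possible dose-sparing effect. Section 2 describes repeated ETEC illness in young children in endemic areas, so some antibody before vaccination is plausible.

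**Working it through.** The SAP states no figure that depends on the ULOQ rule, so there is nothing of its own to reproduce.

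**1. Largest recordable fold rise.** Fold rise is post/baseline, and both are at most ULOQ after capping. The maximum is therefore ULOQ / min(baseline, ULOQ). This needs no ULOQ value.

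| Baseline as a fraction of ULOQ | Largest fold rise |
|---|---|
| 0.25 | 4.0 |
| 0.26 | 1/0.26 = 3.85 |
| 0.50 | 2.0 |
| 0.51 | 1/0.51 = 1.96 |
| 0.80 | 1.25 |
| 1 or more | 1.0 |

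A baseline above ULOQ/2 cannot reach 2-fold and one above ULOQ/4 cannot reach 4-fold. At exactly ULOQ/2 the threshold of section 4.5.2 can still be met. A participant above the ULOQ after both doses gets a dose 2/dose 1 ratio of exactly 1.

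**2. Effect on a ratio between arms.** Inputs:

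- log10 SD s = 0.6. Section 5 gives this for a fold-rise power calculation for CS6; using it as the SD of titres is an assumption.
- True ratio 2.0, the difference named in section 5, so d = log10(2) = 0.301.
- Share of the stronger arm above the ULOQ: not in the SAP, so varied.
- Normal log10 titres, with equal SD in both arms.

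The mean lost to the cap in an arm is s × [φ(z) − z(1 − Φ(z))], where z is the distance from the arm's mean to log10(ULOQ) in SDs. If z is the value for the stronger arm, that for the weaker arm is z + 0.301/0.6 = z + 0.502. The expected ratio is 10^(0.301 − loss in stronger arm + loss in weaker arm).

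| Stronger arm above ULOQ | z stronger / weaker | Loss stronger / weaker (log10) | Expected ratio |
|---|---|---|---|
| 0% | – | 0 / 0 | 2.00 |
| 1% | 2.326 / 2.828 | 0.0020 / 0.0004 | 1.99 |
| 5% | 1.645 / 2.147 | 0.0125 / 0.0034 | 1.96 |
| 10% | 1.282 / 1.783 | 0.0284 / 0.0089 | 1.91 |
| 20% | 0.842 / 1.343 | 0.0670 / 0.0249 | 1.82 |
| 30% | 0.524 / 1.026 | 0.1142 / 0.0476 | 1.72 |

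At 10%, for example, 0.3010 − 0.0284 + 0.0089 = 0.2815, and 10^0.2815 = 1.91.

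**3. Share that cannot be scored as responders.** This also depends on an unstated quantity. Assuming a log10 baseline SD of 0.6, if 1% of baselines exceed the ULOQ, the share above ULOQ/2 is P(Z > 2.326 − 0.502) = 3.4% and above ULOQ/4 is P(Z > 2.326 − 1.003) = 9.3%. If 5% exceed it, the shares are P(Z > 1.645 − 0.502) = 12.6% and P(Z > 1.645 − 1.003) = 26.1%.

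**The case against.** The strongest reply is that nothing shows the ceiling is reached. The SAP states no ULOQ, and the assay range and any repeat at higher dilution may be set in the laboratory procedures, which are not at hand. Sections 2.1 and 4.2 describe these populations as refractory to oral enteric vaccines, which argues against many titres at the limit. The immunogenicity comparisons are secondary and are called exploratory in section 6.8; a fixed rule that errs toward no difference is defensible. The reverse cumulative curves and individual listings would show a ceiling, and a Wilcoxon test is available.

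Most of this stands, and it limits the point to a conditional one. The curves and listings reveal a ceiling but do not correct an estimate, and a Wilcoxon test leaves the capped values tied.

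A reader might infer that the trial's adjuvant and dose contrasts are biased, or that a known fraction of participants cannot respond. The documents support neither: both need a share above the ULOQ that the SAP does not give. A reader might also infer that participants with high baselines should be dropped from the main responder analysis. That would change the estimand to a low-baseline subset, with denominators varying by antigen and threshold in vaccine arms of only 15 outside the infant part.

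**Conclusion.** The point holds in conditional form. That the cap limits the fold rise to ULOQ/baseline is exact and follows from the SAP's own rules. That it pulls GMT and GMFR ratios toward 1 holds when titres exceed the ULOQ and the arms differ by a shift with similar spread. The size cannot be found from the SAP. It is nil if no titre exceeds the limit, small at 1% to 5% of the stronger arm (1.99 to 1.96 for a true 2.0), and material at 20% to 30% (1.82 to 1.72). These figures assume log-normal titres and carry over an SD given for CS6 fold rise. The SAP has an unguarded ceiling; bias in this trial is not shown. It is a cheap improvement to secondary, exploratory analyses and does not touch the primary safety endpoints.

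**What to change.** For any antigen and assay with titres above the ULOQ:

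- Estimate GMTs, GMFRs and their ratios from a normal model on log10 titre that treats those values as right-censored at the ULOQ (for GMT, SAS PROC LIFEREG will do this).
- For fold rise, censor at the participant's own limit, log10(ULOQ/baseline). Where the baseline is itself above the ULOQ, model baseline and post-dose titres jointly.
- Keep the substituted t-test as a sensitivity analysis.
- Keep the planned responder denominators as the main analysis. Report per arm the number above the ULOQ and the number with a baseline above ULOQ/2 and ULOQ/4. Give responder rates without those participants as a sensitivity analysis only.

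The cost is a paragraph in sections 4.5.2 and 8, a few lines of code (somewhat more for the joint model) and extra table rows. Where no titre exceeds the ULOQ, the planned analysis stands. The downside is that the censored model relies on log-normality, which is hard to check in small arms, although the planned t-test already assumes it.

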5 SAMPLE SIZE CONSIDERATIONS

The sample size for this study was selected to detect frequent adverse events. Given a planned sample size of groups of 15 adults, toddlers, and younger children each receiving one of varying dose levels of ETVAX with or without dmLT, the study will have an approximately 80% and 90% chance of observing at least one serious adverse event or adverse event of special interest for events that occur at a rate of 10.3% and 14.3%, respectively. Additionally, if no serious adverse events are observed in 15 participants, the upper bound of the one-sided 95% confidence interval on the rate of serious adverse event occurrence is approximately 18%.

For infant cohorts with 30 participants per dose group, the study will have an approximately 80% and 90% chance of observing at least one serious adverse event or adverse event of special interest for events that occur at a rate of 5.3% and 7.4%, respectively. If no serious adverse events are observed in 30 participants, the upper bound of the one-sided 95% confidence interval on the rate of serious adverse event occurrence is approximately 9.5%.

For infant cohorts, with 30 participants per group, this study is designed to provide approximately 73% power to detect as low as a 2-fold difference in geometric mean fold rise (post-vaccination / baseline) between comparisons of two groups with varying doses of ETVAX and dmLT levels. This power calculation was based on the variability estimate, log10 standard deviation of 0.6, for CS6 obtained from a previous study of the vaccine in Sweden (VAC 003/OEV-121) and two-sample t-test using the 5% two-sided Type I error rate and 10% drop-out rate.

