4.3 Selection of Study Population

This will be a single site study conducted at the Mirpur field site by the icddr,b. The first part (Part A) will enroll a total of 45 adult participants (30 vaccinees and 15 placebos) into one Cohort. The second part (Part B) will enroll a total of 150 toddlers (24-29 months) into 6 separate cohorts to be recruited in step-wise

fashion. Each cohort will enroll 25 toddlers (15 vaccinees and 10 placebos). The third part (Part C) will enroll a total of 100 younger children (12-23 months) into 4 separate cohorts in a step-wise fashion. Each cohort will enroll 25 younger children (15 vaccinees and 10 placebos). The fourth part (Part D) will enroll a total of 200 infants (6-11 months) into 5 separate cohorts to be recruited in a step-wise fashion. Each cohort will enroll 40 infants (30 vaccinees and 10 placebos). Toddlers, younger children and infants will only be enrolled if their parents are fully informed about the study and provide consent for their child's participation.

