	ETVAX Full Dose + 10 μg dmLT vs Placebo	0.xxxx	0.xxxx				
	ETVAX Full Dose vs ETVAX Full Dose + 10 μg dmLT	0.xxxx	0.xxxx				
CS3	ETVAX Full Dose vs Placebo	0.xxxx	0.xxxx				
	ETVAX Full Dose + 10 μg dmLT vs Placebo	0.xxxx	0.xxxx				
	ETVAX Full Dose vs ETVAX Full Dose + 10 μg dmLT	0.xxxx	0.xxxx				
CS6	ETVAX Full Dose vs Placebo	0.xxxx	0.xxxx				
	ETVAX Full Dose + 10 μg dmLT vs Placebo	0.xxxx	0.xxxx				
	ETVAX Full Dose vs ETVAX Full Dose + 10 μg dmLT	0.xxxx	0.xxxx				
CS5	ETVAX Full Dose vs Placebo	0.xxxx	0.xxxx				
	ETVAX Full Dose + 10 μg dmLT vs Placebo	0.xxxx	0.xxxx				
	ETVAX Full Dose vs ETVAX Full Dose + 10 μg dmLT	0.xxxx	0.xxxx				
078 LPS	ETVAX Full Dose vs Placebo	0.xxxx	0.xxxx				
	ETVAX Full Dose + 10 μg dmLT vs Placebo	0.xxxx	0.xxxx				

^{*} Using Holm's-Bonferroni adjustment within each antigen, the p-value is statistically significant.

Programming Note: For each antigen, the Holm's-Bonferroni correction will be performed. If a p-value is statistically significant after the adjustment, a "*" will be placed next to the p-value.

TABLE 14.2.1.3(b): Comparison of Antibody Response to LTB by Antibody Lymphocyte Secretion IgA - Toddlers (24 - 59 Months) Full Analysis Population

		F	P-value from F	value from Fisher's Exact Test						
	Baseline to	Post Dose 1	Baseline to	Post Dose 2	Baseline to A	ny Timepoint				
Comparison	≥2-fold	≥4-fold	≥2-fold	≥4-fold	≥2-fold	≥4-fold				
Comparing Different Doses of ETVAX without dmLT										
ETVAX 1/2 Dose vs ETVAX 1/4 Dose	0.xxxx	0.xxxx								
Comparing ETVAX without dmLT with ETVAX with DMLT										
ETVAX 1/2 Dose vs ETVAX 1/2 Dose + 10 μg dmLT	0.xxxx	0.xxxx								
ETVAX 1/2 Dose vs ETVAX 1/2 Dose + 5 μg dmLT	0.xxxx	0.xxxx								
ETVAX 1/2 Dose vs ETVAX 1/2 Dose + 2.5 μg dmLT	0.xxxx	0.xxxx								
ETVAX 1/4 Dose vs ETVAX 1/2 Dose + 10 μg dmLT	0.xxxx	0.xxxx								
ETVAX 1/4 Dose vs ETVAX 1/2 Dose + 5 μg dmLT	0.xxxx	0.xxxx								
ETVAX 1/4 Dose vs ETVAX 1/2 Dose + 2.5 μg dmLT	0.xxxx	0.xxxx								
Comparing Placebo to ETVAX with and without dmLT										
Placebo vs ETVAX 1/2 Dose	0.xxxx	0.xxxx								
Placebo vs ETVAX 1/4 Dose	0.xxxx	0.xxxx								
Placebo vs ETVAX 1/2 Dose + 10 μg dmLT	0.xxxx	0.xxxx								
Placebo vs ETVAX 1/2 Dose + 5 μg dmLT	0.xxxx	0.xxxx								
Placebo vs ETVAX 1/2 Dose + 2.5 μg dmLT	0.xxxx	0.xxxx								
Comparing different doses of dmLT with ETVAX 1/2 Dose										
2.5 μg dmLT vs 5 μg dmLT	0.xxxx	0.xxxx								
2.5 μg dmLT vs 10 μg dmLT	0.xxxx	0.xxxx								

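### The 73% power stated for a 2-fold GMFR difference between infant groups is wrong: the SAP's own inputs give about 44%

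*SAP*

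**What the plan says.** The last paragraph of SAP Section 5 is the document's only statement of power for the immunogenicity objectives. It begins "For infant cohorts, with 30 participants per group" and goes on to say that "this study is designed to provide approximately 73% power to detect as low as a 2-fold difference in geometric mean fold rise". The contrast is "between comparisons of two groups with varying doses of ETVAX and dmLT levels". The calculation is described as "based on the variability estimate, log10 standard deviation of 0.6, for CS6", an estimate from an earlier study of the vaccine in Sweden, with a "two-sample t-test using the 5% two-sided Type I error rate and 10% drop-out rate".

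The planned analysis matches this. Section 4.3 gives 30 vaccinees in each infant cohort, and Section 8.1.3 compares logs of the fold rise pairwise with a t-test. The error rate does not match. Sections 6.8 and 8 apply a Holm-Bonferroni correction, and the footnote to the infant GMFR comparison shell (Table 14.2.6.1(d)) marks a result with an asterisk to mean "Using Holm's-Bonferroni adjustment within each antigen, the p-value is statistically significant".

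**The concern.** A 2-fold difference is 0.301 on the log10 scale, about half of an SD of 0.6. A two-sided 5% comparison of 27 against 27 at half an SD should have power a little under 50%, so 73% looked too high to be rounding.

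Assessing the adjuvant effect of dmLT is a secondary objective (Section 3.1.2), and dose-sparing is a stated purpose (Section 2.1). The SAP also describes the trial as essential before deciding whether to test efficacy in children. If power is below 50%, a real 2-fold effect in a single dose or dmLT contrast is more likely to be missed than found. A reader told 73% would give a non-significant contrast more weight as evidence of no effect than it can bear.

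**Working it through.** **Inputs, all from SAP Section 5**

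- 30 infants per group with 10% drop-out: 30 × 0.9 = 27 evaluable per group.
- Difference: log10(2) = 0.3010.
- SD: 0.6 on the log10 scale.
- Two-sample t-test, α = 0.05 two-sided.

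**Power from these inputs**

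Standardised difference: 0.3010 / 0.6 = 0.5017.

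Noncentrality: λ = 0.3010 / (0.6 × √(1/27 + 1/27)) = 1.843. Degrees of freedom are 52 and the critical t is 2.007.

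Power = P(|T| > 2.007), with T noncentral t (52 df, λ = 1.843) = **0.440**.

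**Attempts to reproduce 73%**

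| Variant | Power |
|---|---|
| As stated, 27 per group, t-test | 44.0% |
| As stated, normal approximation | 45.4% |
| No drop-out, 30 per group | 48.0% |
| 33 per group | 51.9% |
| One-sided 5%, 27 per group | 56.9% |
| One-sided 5%, 30 per group | 60.9% |
| 27 vaccinees vs 45 pooled placebo | 52.9% |
| One-sample test, n = 27 / n = 30 | 70.9% / 75.7% |
| SD 0.6/√2 = 0.424, 27 per group | 72.5% |
| SD 0.6, 54 evaluable (60 enrolled) per group | 73.3% |

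No variant that keeps to the stated two-group design comes near 73%. The last two rows have the same noncentrality, λ = 2.607. Halving the variance and doubling the group size are the same slip: a factor of 2 missing from the two-sample variance. That is the likely source, but the finding does not depend on it.

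**What 27 per group can detect (SD 0.6, unadjusted two-sided 5%)**

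- 73% power: standardised difference 0.713, or 0.713 × 0.6 = 0.428 log10, which is 2.7-fold.
- 80% power: standardised difference 0.777, or 0.777 × 0.6 = 0.466 log10, which is 2.9-fold.
- To have 73% power at 2-fold: 54 evaluable per group.

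**Effect of the multiplicity rule**

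Table 14.2.6.1(d) lists these infant comparisons for each antigen: 3 between ETVAX doses, 1 between dmLT doses, 6 of ETVAX alone against ETVAX with dmLT, 5 against placebo and 3 combined. The total is 3 + 1 + 6 + 5 + 3 = 18. The first Holm step tests at 0.05/18 = 0.0028, where the critical t on 52 df is 3.141 and power for a 2-fold difference is **11.0%**. Even with the favourable SD of 0.424 it would be 31%.

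**Rest of Section 5**

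The safety figures reproduce. With 15 participants, event rates of 10.3% and 14.3% give 80.4% and 90.1% chances of seeing at least one event. With 30, rates of 5.3% and 7.4% give 80.5% and 90.0%. The zero-event upper bounds are 18.1% and 9.5%. The GMFR power is the only figure that fails.

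**The case against.** The strongest defence concerns the SD. Section 5 does not say whether 0.6 is the SD of a single titre or of the within-child log fold rise. If it is a titre SD and the pre/post correlation is 0.75, the fold-rise SD is 0.6 × √(2 × 0.25) = 0.424 and power is 72.5%. However, the SAP states no correlation and gives 0.6 as the variability behind a GMFR comparison. On that reading an essential input is missing, so the paragraph needs correcting either way.

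Three limits on the finding do stand:

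- **Pairwise contrasts only.** The 44% applies to one arm of 30 against another, which is what Section 5 claims. The combined infant contrast of ETVAX alone against ETVAX with dmLT has 90 against 60 enrolled, or 81 against 54 evaluable. It has about 81% unadjusted power, falling to about 43% at 0.05/18.
- **The 11% is a floor.** It is power at the strictest Holm threshold, and later steps are less severe. The family of 18 assumes that each time column of the shell is adjusted separately within an antigen, which the SAP does not spell out.
- **Limited reach.** The sample size was chosen for safety, the immunogenicity comparisons are labelled exploratory, and the SAP nowhere proposes to read non-significance as equivalence. No planned test, estimate or interval changes.

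The exploratory label does not justify a wrong figure, since power is what a reader needs in order to weigh a null result.

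**Conclusion.** The stated 73% is wrong. From the inputs printed in Section 5, power for a 2-fold GMFR difference between two infant groups is 44.0%, or 48.0% without drop-out. The overstatement is 73 − 44 = 29 percentage points. The difference detectable with 73% power is 2.7-fold, not 2-fold. Adjusted power is lower, down to about 11% at the first Holm step.

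This rests on taking 0.6 as the SD of the log10 fold rise, which is how Section 5 uses it, and on 27 evaluable infants per group. It concerns the pairwise dose and dmLT contrasts. The safety figures and the basis for the sample size are unaffected.

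**What to change.** Replace the power sentence in Section 5 with wording such as: *With 30 infants per group (27 evaluable after 10% drop-out), a log10 SD of 0.6 for the fold rise and an unadjusted two-sided 5% t-test, power is about 44% for a 2-fold difference in GMFR between two groups and 80% for a 2.9-fold difference. Power after Holm-Bonferroni adjustment is lower, about 11% for a 2-fold difference at the first step with 18 comparisons.*

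Before finalising, check the 0.6 against the earlier study. If it is a titre SD, state the assumed pre/post correlation and its source, and recompute. A sentence saying that a non-significant pairwise contrast is not evidence of equivalence would help readers, but the correction does not depend on it.

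The cost is one paragraph and a less favourable number. No participants, analyses or table shells change.
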